to implementation.³³ Factors included in this study are informed by previous school-based research and input from community partners at GISD and MI DHHS; this includes constructs related to the intervention (e.g., packaging/manual), context (e.g., implementation climate) and providers (e.g., knowledge and beliefs).³² The implementation outcome is dose delivered: a fidelity dimension. 12 We assess dose delivered by asking about the proportion of the MMH curriculum teachers reported delivering to students, from 0: none to 4: 75% or more. The measure is consistent with dose delivered in a previous study of MMH.²⁸ The semi-structured interviews focus on the intervention, context, and provider characteristics, including barriers and facilitators to MMH delivery. Data Analysis: Quantitative data analysis: We will use multinomial logistic regression models to estimate the probability of an outcome relative to a baseline category for a given set of predictors. 58 We will account for nesting by school as needed; our community partners indicate, however, that many high schools in Michigan are staffed by one certified health teacher. Guided by Hosmer and Lemeshow's approach, 59 we will choose variables for inclusion based on statistical and substantive contributions to the overall model.⁵⁹ In the interest of parsimony and reducing model over fitting, we will use both theoretical considerations and the Wald test to eliminate variables that do not contribute to the model. Qualitative Data analysis: We will analyze

the structured interviews using N-vivo. First, we will mark separate segments responses that represent distinct constructs. Next, we will review data chunks to establish agreement and then assign chunks into meaningful categories guided by CFIR. Next, we will combine categorized data chunks. Finally, we will review data to identify common themes. Results from qualitative data analysis will inform model building and provide context for interpreting and applying quantitative results. **Expected outcomes:** We expect to identify specific factors across CFIR domains that influence dose delivered.³³ For example, we may find that teachers report MMH is not fully meeting students' needs around substance use and that this is associated with less dose delivered. These results will be critical to informing REP for the pilot study (Aim 3).

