Aim 3: MMH REP pilot: building on the skills developed in Aim 1 and Training Goals 1-3, I will conduct a prospective implementation pilot of the MMH in the GISD. REP is well suited for implementing MMH because it includes a curriculum manual and teacher training processes. The overall purpose of this pilot is to assess the appropriateness, feasibility, and acceptability of using REP for MMH, a universal ATOD prevention program. 62 I will create a customized package for delivering MMH using standard and enhanced REP. Informed by data from Aim 1, I will investigate the effectiveness of standard and enhanced REP on implementation and behavioral outcomes. Sample and setting. We will study high schools from Genesee County, MI. Like other communities facing declining populations and economic challenges, the county has had higher unemployment levels compared to state and national averages for over a decade, 66 and youth report higher rates of ATOD use compared to state averages (Table 6). This pilot study will include 8 schools from the Genesee Intermediate School District (GISD), as informed by other implementation pilot studies⁶² and study resource limitations. GISD includes 21 school districts and 25 public high schools. In collaboration with GISD partners, we will identify high schools using MMH that fail to meet MI DHHS standards for implementation (75% or less of the curriculum) to contact regarding participation. We will select schools using data from our MMH implementation study that have comparable student demographics (e.g., % free/reduced lunch). Procedures. We will recruit schools in collaboration with GISD leadership. Identified schools will be randomized to either standard REP or enhanced REP (see Table 3). The standard REP condition will receive a customized MMH manual (adapted from the current manual) based on results from Aim 2 to meet the needs of the context and providers; this may include creating on online manual. Standard REP will also include customized training based on Aim 2 (e.g., adapting content to new substances or substance forms, updated teacher resources) and brief, as needed technical assistance. Enhanced REP will also include internal and external facilitators with specific expertise in health education and implementation with weekly teacher contact to provide specific guidance for overcoming MMH delivery barriers. Enhanced REP will also include additional training and packaging customization (e.g., supplemental ATOD resources). The study team will meet with teachers and parents at participating schools to share study information. Teachers will complete a survey on MMH implementation and using Enhanced REP to deliver MMH post-intervention. We will also conduct qualitative interviews of teachers in participating schools to obtain in-depth information about using MMH delivery with REP. Students receiving the MMH at participating schools will be eligible for student-level surveys. Students will be recruited in participating schools in conjunction with GISD partners. Following parental consent and participant assent, students will complete a self-administered questionnaire through a secure, online survey about ATOD and related behaviors. As MMH is integrated as part of the school curriculum, students will complete the initial survey during their 9th or 10th grade health class prior to MMH delivery and 3 months postdelivery. Students who do not consent will receive an alternate activity. I expect 300 students to participate based on a 60% response rate. 67 Students will receive \$10 for the surveys.

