
Aim 3b: Procedures. Guided by Costs of Implementing New Strategies (COINS), we will monitor the activities listed in Table 7 to estimate implementation strategy costs. The study team will track time for labor costs-most of the resource/costs. This will include tracking time in study team activities as well as time logs for community partners to track REP activities. The study team will also track and compile all non-labor costs. **Measures.**Costs: Implementation cost measures are guided by COINS and include indirect and non-labor costs. We will measure implementation costs using available cost data from the school district, summary data from previous empirical studies on implementation costs, and routinely available cost data using market prices. 45

Table 7: Intervention costs informed by Costs of Implementing New Strategies (COINS)

Phases	Description	Activities	Resource/cost type
Pre-	-		
implementation	Identify barriers	Stakeholder meetings	RF, PM/ labor costs
		Survey	Secondary data, PM, RF/labor cost
		Interviews	Secondary data, PM, RF/labor cost
	Draft package	Identify adaptations	RF, CP/ labor costs
		Identify core elements	RF, CP/ labor costs
		Program adaptations: online	P/ labor costs
			domain costs/nonlabor
		Program adaptations: manual	PM, RA/ labor costs
	Pilot test package	refinement	RF, RA, PM/ labor costs
	Orientation	identify schools	RF, PM, CP/ labor costs
		Logistics of delivery	RF, PM/ labor costs
		Refine training	RF, CP/ labor costs

		Identify EF IF	CP/ labor costs
	Training	Staff training: intervention	RF. CP/ labor costs
			travel costs, RF/nonlabor
			training compensation/nonlabor
			space/nonlabor
Implementation			hosting/nonlabor
		Disseminate package	PM/labor costs
	Technical assistance	Internal facilitation	CP/ labor costs
		External facilitation	PM/labor costs
	Evaluation	Interviews	RF, RA/labor costs
			remuneration/nonlabor
		Survey	RF, RA/labor costs
			remuneration/nonlabor
	Refinement	Analyze data	Secondary data, PM, RF/labor costs
		training, package refinement	PM, RF, CP/labor costs
	Organizational		
Sustainability	changes	Recommendations for REP	PM, RF, CP/labor costs
		Reproduce package	CP/ labor costs
		Continue to refine	CP, RF/labor costs

PM: project manager; RA: research assistant; RF: research faculty, CP: community partner, P: programmer Table adapted from Saldana et al¹⁴

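### Table 7 puts no cost on teacher time spent receiving facilitation, so from a school or societal perspective the incremental cost of enhanced REP is understated by the between-arm difference in that time

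*Combined protocol and SAP*

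**What the plan says.** Under Aim 3b, Procedures, cost capture is tied to one inventory: "we will monitor the activities listed in Table 7 to estimate implementation strategy costs". Labor is described there as the bulk of the cost, and the people whose time is tracked are named: "This will include tracking time in study team activities as well as time logs for community partners to track REP activities".

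In Table 7 the two facilitation rows read "Internal facilitation CP/ labor costs" and "External facilitation PM/labor costs". The legend is "PM: project manager; RA: research assistant; RF: research faculty, CP: community partner, P: programmer". No code stands for a teacher.

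Aim 3, Sample and Procedures, sets the contrast between the arms. Enhanced REP adds internal and external facilitators "with weekly teacher contact to provide specific guidance for overcoming MMH delivery barriers"; standard REP offers "brief, as needed technical assistance". Table 3 also has the internal facilitator meeting regularly with providers.

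The Aim 3b Data Analytic Approach takes Cost(E-REP) minus Cost(REP) as the numerator of the incremental cost-effectiveness ratio (ICER). It plans one-, two- and three-way sensitivity analyses on the input parameters.

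**The concern.** A facilitation contact uses the time of at least two people: the one who gives the help and the teacher who receives it. The inventory counts only the first. A school that adopts enhanced REP has to supply the second every week of delivery. The Significance section itself argues that cost shapes delivery in schools because their resources are tightly allocated.

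A cost left out of both arms equally would drop out of the numerator. This one does not, because the amount of teacher contact is part of what distinguishes the arms. If enhanced REP does reduce ATOD use relative to standard REP, a numerator that is too small makes the ICER look better than it is. That is the direction of the expectation stated at the end of Aim 3b.

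**Working it through.** The documents give no hours, wage, cost or ICER, so there is no figure to reproduce. The check is a reading of the inventory followed by an illustration of size.

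**Step 1: is teacher time in the inventory?**

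- Facilitation rows of Table 7: community-partner labor (internal) and project-manager labor (external). Teacher entries: 0.
- Other rows that could pay teachers: training compensation, and remuneration for the evaluation interviews and survey. These are different activities from receiving facilitation.
- Time tracking: study team and community partners. In Aim 2, Measures, the latter term appears as "input from community partners at GISD and MI DHHS". Aim 2, Sample and setting, lists teachers as participants. The Aim 3 progress note plans facilitation training for health coordinators, so the internal facilitator is not evidently the classroom teacher.
- Aim 3 and Aim 3a give teachers a survey, interviews and lesson checklists, but no time log.

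Following the text, teacher time in facilitation is valued at zero.

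**Step 2: does it cancel between arms?** Let T be the value of teacher time in facilitation or technical assistance, per arm. Then

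(true incremental cost) − (planned incremental cost) = T(E-REP) − T(REP).

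This is positive whenever weekly contact takes more teacher time than as-needed help.

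**Step 3: would the planned analyses reveal it?** The sensitivity analyses vary the inputs. An item that is not an input is not varied.

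**Step 4: size, on assumed values.** The eight schools are in the plan. A 4:4 split, the number of weeks, the contact length and the wage are assumptions. One teacher per school is also an assumption, though Aim 2 reports this as common in Michigan high schools.

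- Hours = schools × teachers × weeks × hours per contact = 4 × 1 × 12 × 0.5 = 24, up to 4 × 1 × 18 × 0.5 = 36.
- Value at $40 an hour: 24 × 40 = $960, up to 36 × 40 = $1,440.
- Per enhanced school: 960 / 4 = $240, up to 1,440 / 4 = $360.

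If standard-arm teachers spend 25% or 50% as much time on as-needed help, the net figure per enhanced school is:

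- 25%: 0.75 × $240 to 0.75 × $360 = $180 to $270
- 50%: 0.50 × $240 to 0.50 × $360 = $120 to $180

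Wider assumptions (8 to 18 weeks, 0.25 to 1 hour, $30 to $60 an hour):

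- Low: 4 × 1 × 8 × 0.25 = 8 hours; × $30 = $240 in total, or $60 per enhanced school.
- High: 4 × 1 × 18 × 1 = 72 hours; × $60 = $4,320 in total, or $1,080 per enhanced school.

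Both are before any standard-arm offset.

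**The case against.** The strongest reply is that the exclusion of teachers is an inference. Table 7 does not define community partner, and the Potential Problems section also speaks of partners in local school districts. Aim 3b says that costs include indirect costs and may draw on school-district cost data. Aim 1b, which uses the same table, lists training compensation and time spent assisting with delivery. All this leaves room for school staff time. None of it names the teacher's time in receiving facilitation, though, and no row or log would collect it. The ambiguity is real, but it does not put the cost into the plan.

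A second reply is that no costing perspective is stated. Under a narrow budget perspective, salaried minutes within the school day might properly be left out. That stands, and it is why the conclusion is tied to a school or societal perspective. Costing community-partner time sits awkwardly with the narrow reading, but does not settle the matter.

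Third, if the planned logs record the length of each contact, one-to-one teacher time could be approximated later. That is possible, but the text does not say the logs will hold contact durations or attendance.

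Finally, a reader might infer that this cost falls on the enhanced arm alone. The documents do not support that: standard-arm teachers also give uncosted time to as-needed help. Only the difference between arms biases the numerator.

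**Conclusion.** The point holds in a limited form. As written, teacher time in facilitation enters at zero. From a school or societal perspective, the incremental cost of enhanced REP is understated by the between-arm difference in teacher time, provided weekly contact takes more of it than as-needed help.

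The direction follows from the text; the size does not. The illustration of $240 to $360 per enhanced school is gross of standard-arm time and rests on assumed contact length, weeks, wage, teachers per school and allocation.

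A reader might note that the teacher is one of two people at a contact with one facilitator, or one of three with both, and infer that 33% to 50% of the cost is missing. That is a share of contact person-hours. It is not a share of incremental cost, which also includes the extra training and packaging customization. No total is given against which to judge materiality, so the documents do not show that the ICER would change a decision. The gap is worth closing because it has a known direction, escapes the planned sensitivity analyses and is cheap to repair before the pilot.

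**What to change.** - State the costing perspective in Aim 3b, and say whether community partner includes teachers.
- Add a teacher labor category to the facilitation and technical assistance rows of Table 7, applied in both arms. Add it to training only where the time is not already covered by training compensation.
- Record teacher minutes per contact on the study-team and community-partner time logs already planned, including as-needed contacts in the standard arm.
- Value those minutes at the district wage in the base case, and report the ICER without teacher time as a sensitivity analysis.

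The cost is one extra log field and, probably, a slightly higher reported cost for enhanced REP. The Aim 3 progress note says that the implementation guide is still being designed and the pilot is planned for early 2021, so the minutes can be collected prospectively. They would be hard to recover afterwards.

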Data Analytic Approach. I will report summary statistics for implementation costs including mean costs with 95% confidence intervals. All costs will be adjusted to current year US dollars. I will estimate costs of REP and E-REP using the cost data, with the comparator strategy being REP. The outcome will be change in reported

ATOD use. I will use net costs (net increase in costs from E- REP compared to REP) and net effectiveness (net decrease in ATOD use for E-REP versus REP) to calculate the incremental cost-effectiveness ratio for

student outcomes: $\frac{Cost_{E-REP} - Cost_{REP}}{Outcome_{ATOD\ use\ E-REP} - Outcome_{ATOD\ use\ REP}}$. I will conduct a one-way sensitivity analysis on all

input parameters to provide estimates of the costs and incremental cost-effectiveness to decision-makers. The analysis will include 2- and 3-way sensitivity analyses on the parameters most sensitive in influencing the cost-effectiveness ratio. Expected outcome: I expect that students in the enhanced REP condition will report greater reduction in ATOD use relative to dollar spent on the implementation strategy compared to those in standard REP.

Missing data. We will conduct tests of selective attrition as needed to explore if those lost to follow up and with missing data on outcomes differ from those retained. In addition, we will use approaches such as multiple imputation and full-information maximum likelihood as needed to address missing values on model predictors to avoid biases due to complete case analysis.⁷⁴ Full-information maximum likelihood and multiple imputation are both preferred over deletion approaches or nonstochastic imputation methods (e.g., mean imputation).^{74,75}

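### Table 7 feeds survey and interview payments and evaluation labor into the estimated strategy costs, and the plan has no rule separating research-only cost from the cost of REP or E-REP

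*Combined protocol and SAP*

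**What the plan says.** Under Aim 3b, Procedures, the link between Table 7 and the cost estimate is direct: "we will monitor the activities listed in Table 7 to estimate implementation strategy costs". Two sentences on tracking set its scope: "This will include tracking time in study team activities as well as time logs for community partners to track REP activities", and "The study team will also track and compile all non-labor costs".

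In Table 7, the Evaluation entry has an Interviews row and a Survey row. Each carries research faculty and research assistant time ("RF, RA/labor costs") and a separate payment line ("remuneration/nonlabor"). The Refinement entry that follows has a row for analyzing data, resourced as "Secondary data, PM, RF/labor costs", next to a row for refining the training and package.

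The Aim 3b Data Analytic Approach then commits to an absolute cost output: "I will report summary statistics for implementation costs including mean costs with 95% confidence intervals". It also estimates the costs of REP and E-REP from the same data and uses their difference as the numerator of the incremental cost-effectiveness ratio (ICER). The results are meant for decision-makers. No costing perspective (district, payer or societal) is stated.

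**The concern.** A strategy's cost should be what it takes to deliver the strategy. Table 3 describes standard REP as packaging, training and facilitation, with monitoring of uptake under facilitation. The Aim 3 student surveys ask about substance use and related behaviors. They supply the trial's behavioral outcome and the denominator of the ICER. Paying for and administering that measurement is not in Table 3 for either strategy.

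If such items stay in, the mean cost of each strategy is overstated for anyone using it to plan delivery outside a study. A common amount added to both strategies also makes E-REP look relatively less expensive than it is, although the difference in dollars is unchanged.

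**Working it through.** The documents give no cost total, mean cost or ICER, so there is no figure to reproduce. The check has two parts.

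**Is research cost separated anywhere?**

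- Aim 3b Procedures cost the activities of Table 7 and exclude no row.
- Study-team time and all non-labor items are tracked, with no instruction to split research time from implementation time.
- Aim 1b, Measures, gives examples of implementation cost: training, supervision, help with delivery, materials, technical assistance, facilitator time and travel. Payments for completing surveys or interviews are not among them. That list refers to Table 7 and is not said to be complete, so it supports the point without settling it.
- Table 7 treats payments unevenly. Aim 2 survey participants received $10, yet the pre-implementation Survey row has no payment line, while the Evaluation Survey row has one. No stated rule explains the difference.

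So nothing separates the two kinds of cost.

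**How large is it?** Only survey payments can be priced, and Table 7 does not say whose survey is meant. Aim 3 has a teacher survey and a student survey.

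Inputs from Aim 3: 8 schools; $10 to students for the surveys (not stated whether once or each time); two student surveys; and "I expect 300 students to participate based on a 60% response rate".

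| Reading of the Survey payment line | Total | Per school (total / 8) |
|---|---|---|
| Students, paid once | 300 × $10 = $3,000 | $375 |
| Students, paid at both surveys | 300 × $10 × 2 = $6,000 | $750 |
| Teachers only (assumed: one per school, $10 as in Aim 2) | 8 × $10 = $80 | $10 |

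The student readings come to $10 or $20 per participating student. Interview payments have no stated amount, and evaluation labor and data analysis have no hours or rates, so none of these can be priced.

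**Effect on the difference.** With student numbers a in E-REP and 300 − a in REP, and k payments of $10, the E-REP minus REP total shifts by (a − (300 − a)) × $10 × k.

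- a = 150: shift $0.
- a = 200 (assumed imbalance): (200 − 100) × $10 × k = $1,000 for k = 1 and $2,000 for k = 2. With an assumed 4 schools per arm, that is $250 to $500 per school.
- a = 100: the same amounts with the opposite sign.

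**Effect on the ratio.** Adding a common cost c to both strategies turns E/R into (E + c)/(R + c), which is smaller whenever E > R. For illustration only, with assumed costs per school of R = $2,000 and E = $4,000 (true ratio 2.0):

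- c = $375: 4,375 / 2,375 = 1.84.
- c = $750: 4,750 / 2,750 = 1.73.
- c = $10: 4,010 / 2,010 = 1.995, practically no change.

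**The case against.** The case on the other side has five parts.

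- **Whose survey.** The Survey row sits beside Interviews, and the Aim 3 interviews are with teachers only. A teacher-survey reading is at least as natural as a student one. This stands: the $375 to $750 is conditional, and the low end is about $10 per school.
- **Data analysis.** A reader might infer that the data-analysis row is purely research. The documents do not support that. It belongs to Refinement, next to training and package refinement, and Table 3 makes monitoring by qualitative and quantitative data part of standard REP. Some of this row, and some evaluation labor, may be genuine strategy work.
- **Who pays.** A reader might infer that a school district would never bear these costs. No perspective is stated and nothing says who would pay, so that cannot be shown. It is itself a reason to state the perspective.
- **The ICER.** A reader might infer that the cost-effectiveness ratio is biased. Costs equal in both arms cancel in its numerator, so any effect depends on imbalance between arms.
- **Separability.** Table 7 is already itemized and payments have their own lines, so an analyst could drop them later. That holds for payments. It does not hold for staff time logged without a purpose, and Aim 3b says labor is most of the cost. The planned one-way sensitivity analyses vary input values; they do not define which inputs belong.

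**Conclusion.** The concern holds for the absolute mean costs. As written, they would include survey and interview payments and evaluation labor, with no rule to take out the part that serves only to measure trial outcomes. The identifiable amount runs from about $10 per school (teachers only, assumed $10 and one teacher per school) to $375 or $750 per school (all 300 students, paid once or twice), with interview payments and labor on top and unpriced. The E-REP minus REP difference changes by $0 from student payments when student numbers are equal, and by $1,000 to $2,000 in total under an assumed 200/100 split.

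This is a modest, inexpensive improvement to a planned output of a pilot. It does not invalidate the cost analysis.

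**What to change.** State the costing perspective in Aim 3b, and say whose survey and interviews the Table 7 payment lines cover.

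Before time tracking starts, tag each Table 7 line as strategy or research-only. Split the mixed rows, namely Evaluation and the data-analysis row: uptake monitoring and package refinement stay in strategy cost, while participant payments and outcome-measurement labor go to research-only. Base the main mean costs and the ICER on the strategy lines. Report the research-only total separately, so that mean costs are shown with and without it.

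The price is one extra column in the cost log and some judgement in dividing mixed rows. Timing matters because pooled study-team hours are hard to divide afterwards.
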